2.3. Study Design

Overview of Study Design and Key Features

The study design schematic is shown in [Figure 1](#).

Figure 1 Study Design Schematic

BID=twice daily; PK=pharmacokinetic; TOC=test of cure; WBC=white blood cell.

- Serial blood PK sampling will be performed for the first dose of study treatment on Day 1 and for the time-matched dose on Day 4. Blood samples will be collected predose and at 0.5, 1, 1.5, 2, 3, 4, 6, 8, and 12 hours postdose.
- Serial urine PK sampling will be performed for the first dose of study treatment on Day 1 and for the time-matched dose on Day 4. Urine samples will be collected predose and at intervals of 0 to 2 hours, 2 to 4 hours, 4 to 6 hours, 6 to 8 hours, 8 to 10 hours, and 10 to 12 hours postdose.
- Predose PK blood samples will be collected before each time-matched dose on Days 1 through 5. Predose PK urine samples will be collected 0 to 2 hours before each time-matched dose on Days 1 through 5. Only 1 sample is needed when serial and predose samples overlap.

Participants will check-out of the clinic after all study procedures have been performed, including a predose clean-catch midstream urine sample for Gram stain, quantitative bacteriology culture, and antimicrobial susceptibility testing, predose PK sample collections, and safety assessments. Participants should remain in the clinic to complete a total of 10 doses. Participants will be instructed to return for the TOC (Day 10 to 13) and Follow-up (Day 28±3) Visits

Design Features	
 • A Phase IIa single-center, open-label, repeat dose PK study. • The study duration is approximately 28 days comprising approximately 5 days of confinement at the clinic followed by 2 outpatient visits 
 ○ Clinic Confinement Visits 
 ▪ Baseline (Day -1 to Day 1 predose) Visit ▪ On-Therapy (Day 1 to Day 5) Visit ○ Outpatient Visits 
 ▪ TOC (Day 10 to 13) Visit ▪ Follow-up (Day 28) Visit • Approximately 25 to 30 participants will be enrolled to achieve approximately 20 participants who complete the study assessments through Day 5 and are evaluable for the PK analyses.
------------------------	--

Dosing	
 All participants who meet the study entry criteria and provide informed consent will receive oral gepotidacin 1500 mg (2 × 750-mg tablets) BID for 5 days (total of 10 doses).
Time & Events	
 Refer to Appendix 1: Schedule of Activities
Treatment Assignment	
 This is a nonrandomized, open-label study. Clinic personnel will enroll the participant into the study once a participant has met all eligibility requirements.
Interim Analysis	
 No interim analyses are planned for this study.

2.4. Statistical Hypotheses

A formal hypothesis will not be tested; however, an estimation approach will be taken to characterize the PK of gepotidacin in female participants with uncomplicated urinary tract infection (UTI).

3. PLANNED ANALYSES

3.1. Final Analyses

The final planned primary analyses will be performed after the completion of the following sequential steps:

1. All participants have completed the study as defined in the protocol at Follow-up Visit.
2. All required database cleaning activities have been completed and final database release (DBR) and database freeze (DBF) has been declared by Data Management.

4. ANALYSIS POPULATIONS

Population	Definition / Criteria	Analyses Evaluated
Safety	
 All participants who take at least 1 dose of gepotidacin. 	
 Study Population Safety
PK	
 All participants in the Safety Population and have evaluable plasma, urine, or tissue concentration data for gepotidacin. A subject is considered to have evaluable PK data for gepotidacin if the subject has at least 1 measurable post-dose PK concentration value for gepotidacin that was not excluded from the analysis due to a protocol deviation. This primary analysis population will be used in the assessment and characterization of PK concentrations (summary tables, listings, and figures) 	
 PK Concentration
PK Parameter	
 All participants in the PK Population who receive gepotidacin 1500 mg BID through the completion of all PK collections for whom valid and evaluable plasma or urine PK parameters are derived for gepotidacin. This primary analysis population will be used in the assessment and characterization of PK parameters (summary and analysis tables, listings, and figures) 	
 PK Parameter
Intent-To-Treat (ITT)	
 All participants that met all eligibilities and were assigned to study treatment 	
 Study Population
Microbiological ITT (micro-ITT)	
 All participants in the ITT Population, receive at least 1 dose of gepotidacin, and have a qualifying baseline uropathogen from a quantitative bacteriological culture of a pretreatment clean catch midstream urine specimen. The algorithm of the qualifying bacterial uropathogen is presented in Appendix 4: Derived and Transformed Data, Figure 2. 	
 Efficacy
PKPD	
 All participants in both the PK Parameter Population and the Micro-ITT Population 	
 PKPD

Refer to [Appendix 9: List of Data Displays](#).

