- Assessments scheduled at the same nominal time should occur in the following order: electrocardiogram, urine collection, blood collection. The timing of the assessments should allow the blood draw to occur at the exact nominal time.
- Obtain single 12-lead electrocardiogram in semi-supine position at predose and 2 hours postdose on Days 1 and 4. The predose and postdose electrocardiogram time points should be the same on both days.
- Only repeat the electrocardiogram assessment at predose on Day 1 if it was not performed within 4 hours of the baseline assessment.
- Study treatment will be administered under site staff supervision and with food (i.e., standardized meals or snacks as applicable). On Days 1 and 4, for the dose associated with serial PK collections, participants should be in a semi-supine position for approximately 3 hours after study treatment administration with only minor exceptions (e.g., urine PK collections).
- Collection of the PK samples should occur before this dose is administered.
- Blood PK samples will be collected at predose and 0.5, 1, 1.5, 2, 3, 4, 6, 8, and 12 hours postdose for the first dose of study treatment on Day 1 and for the time-matched dose on Day 4.
- Urine PK samples will be collected predose and at intervals of 0 to 2 hours, 2 to 4 hours, 4 to 6 hours, 6 to 8 hours, 8 to 10 hours, and 10 to 12 hours postdose for the first dose of study treatment on Day 1 and for the time-matched dose on Day 4.

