- Serial blood PK sampling will be performed for the first dose of study treatment on Day 1 and for the time-matched dose on Day 4. Blood samples will be collected predose and at 0.5, 1, 1.5, 2, 3, 4, 6, 8, and 12 hours postdose.
- Serial urine PK sampling will be performed for the first dose of study treatment on Day 1 and for the time-matched dose on Day 4. Urine samples will be collected predose and at intervals of 0 to 2 hours, 2 to 4 hours, 4 to 6 hours, 6 to 8 hours, 8 to 10 hours, and 10 to 12 hours postdose.
- Predose PK blood samples will be collected before each time-matched dose on Days 1 through 5. Predose PK urine samples will be collected 0 to 2 hours before each time-matched dose on Days 1 through 5. Only 1 sample is needed when serial and predose samples overlap.
- Participants will check-out of the clinic after all study procedures have been performed, including a predose clean-catch midstream urine sample for Gram stain, quantitative bacteriology culture, and antimicrobial susceptibility testing, predose PK sample collections, and safety assessments. Participants should remain in the clinic to complete a total of 10 doses. Participants will be instructed to return for the TOC (Day 10 to 13) and Follow-up (Day 28±3) Visits.

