5.2. Number of Participants

Approximately 25 to 30 participants will be enrolled to achieve approximately 20 participants who complete the study assessments through Day 5 and are evaluable for the PK analyses.

If participants prematurely discontinue the study, additional replacement participants may be recruited at the discretion of the sponsor and in consultation with the investigator.

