10.1. Sample Size Determination

The target sample size is approximately 20 participants who complete the study assessments through Day 5. The sample size for this study was based on feasibility; however, justification has been considered. Gepotidacin 1500 mg BID PK parameter estimates are available from a healthy volunteer study with repeat dosing for 14 days. For this dose of gepotidacin, the coefficient of variations for AUC(0- τ) and C_{max} were 21.9% and 40.3%, respectively, after the initial dose, and 29.6% and 31.1%, respectively, at steady state. The upper limit of the 95% confidence interval for the mean of the PK parameters on both Days 1 and 4 for AUC(0- τ) and C_{max} will be approximately within 15% and 20%, respectively, above the point estimate of the corresponding PK parameter.

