10.2. Populations for Analyses

For purposes of analysis, the following populations are defined:

Population	Description
PK Population	Participants who receive at least 1 dose of gepotidacin and have evaluable plasma, urine, or tissue concentration data for gepotidacin. This primary analysis population will be used in the assessment and characterization of PK concentrations (summary tables and figures).
PK Parameter Population	All participants in the PK Population who received gepotidacin 1500 mg BID through the completion of all PK collections for whom valid and evaluable plasma or urine PK parameters are derived for gepotidacin. This primary analysis population will be used in the assessment and characterization of PK parameters (summary and analysis tables and figures).
Intent-to-Treat (ITT) Population	All participants assigned to study treatment.
Microbiological ITT (micro-ITT) Population	All participants assigned to study treatment who receive at least 1 dose of gepotidacin have a qualifying baseline uropathogen (as defined in Appendix 9) from a quantitative bacteriological culture of a pretreatment clean catch midstream urine specimen.
Safety	All participants who take at least 1 dose of gepotidacin.

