10.3. Statistical Analyses

10.3.1. Pharmacokinetic Analyses

Endpoint	Statistical Analysis Methods
Primary	
 The primary endpoints of this study are PK-related. The analysis for the primary PK endpoints will be performed for the PK Parameter Population. Plasma concentrations of gepotidacin will be subjected to PK analyses using noncompartmental methods. Based on the individual concentration-time data the following plasma parameters will be estimated: 
 Day 1 (first dose): AUC(0-τ), C_{max}, and t_{max} Day 4 (repeat dose): AUC(0-τ), C_{max}, t_{max}, CL_{ss}/F, and R_o Days 1 through 5 (predose): C_{τ} Summary statistics (arithmetic mean, geometric mean, median, standard deviation, minimum, maximum, and coefficient of variation) for plasma

Endpoint	Statistical Analysis Methods
	gepotidacin PK parameter values will be summarized by study day, as appropriate. The C_{τ} will be summarized and used to assess achievement of steady state. Gepotidacin plasma PK parameter estimates will be listed by participant and study day. Individual plasma gepotidacin PK parameter estimates will be plotted by day on linear scales.
Secondary	
 • The analysis for the secondary PK endpoints will be performed for the PK Parameter Population. Urine concentrations of gepotidacin will be subjected to PK analyses using noncompartmental methods. • Based on the individual concentration-time data the following urine parameters will be estimated: 
 – Day 1 (first dose): Ae 12h, Ae(t1-t2), fe%, and CLr – Day 4 (repeat dose): Ae 12h, Ae(t1-t2), fe%, and CLr – Days 1 through 5 (predose): C_{τ} • Summary statistics (arithmetic mean, geometric mean, median, standard deviation, minimum, maximum, and coefficient of variation) for urine gepotidacin PK parameter values will be summarized by study day, as appropriate. The C_{τ} will be summarized and used to assess achievement of steady state. Gepotidacin urine PK parameter estimates will be listed by participant and study day. Individual urine gepotidacin PK parameter estimates will be plotted by day on linear scales

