7.1.3. Population of Interest

The primary pharmacokinetic analyses will be based on the Pharmacokinetic population and Pharmacokinetic Parameter population, unless otherwise specified.

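### The PK Parameter Population requires dosing through all PK collections, so completed Day 1 parameters from participants who stop early are left out of the primary and secondary PK summaries

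*SAP*

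**What the plan says.** SAP section 4 draws the PK Parameter Population from the wider PK set and keeps only those "who receive gepotidacin 1500 mg BID through the completion of all PK collections for whom valid and evaluable plasma or urine PK parameters are derived". Protocol 10.2 carries the same restriction (participants "who received gepotidacin 1500 mg BID through the completion of all PK collections"), so the SAP did not introduce it.

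Protocol 10.3.1 applies the set to the primary endpoints: "The analysis for the primary PK endpoints will be performed for the PK Parameter Population". It does the same for the secondary urine endpoints. In SAP Appendix 9, the parameter summaries (Tables 4.4 and 4.5) and parameter listings (Listings 40 and 41) use this population only. SAP 7.1.3 says that the primary PK analyses "will be based on the Pharmacokinetic population and Pharmacokinetic Parameter population, unless otherwise specified", without assigning parameters or days to either set.

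On timing, Protocol section 2 places blood samples at "0.5, 1, 1.5, 2, 3, 4, 6, 8, and 12 hours postdose for the first dose of study treatment on Day 1", with urine intervals over the same 12 hours. The collections that close the schedule are the predose ones; Protocol 5.1 says of blood: "Predose PK blood samples will be collected before each time-matched dose on Days 1 through 5". Protocol 8.1.3 rules out a temporary stop, so a participant who stops cannot later satisfy the definition.

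**The concern.** The primary endpoints include Day 1 AUC(0-τ), Cmax and tmax; the secondary ones include Day 1 Ae, fe% and CLr. All of these are fixed by the first 12 hours, and later dosing cannot invalidate them. The definition nevertheless makes their use depend on dosing up to Day 5 predose.

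Two things are at stake. The Day 1 estimates rest on fewer participants than the data allow. They also rest on a subset selected after the first dose. Reasons for stopping listed in Protocol 8.1 include adverse events and lack of efficacy, and 8.1.2 adds QTc criteria. A link between stopping and exposure is therefore plausible, and no planned display would show its effect on the Day 1 parameters.

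**Working it through.** **Step 1. Who is left out**

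- Stops on Day 2 or 3, or on Day 4 before serial sampling ends: the Day 1 profile is complete, but the participant is outside the population. Her Day 1 parameters are absent from Tables 4.4 and 4.5 and Listings 40 and 41.
- Stops after the Day 4 12-hour sample but before the Day 5 predose draw: both profiles are complete, and both are left out.
- In each case the concentrations stay in the PK Population displays (for example Table 4.1, Figure 4.1 and Listings 37 and 38).

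**Step 2. The plan's own precision figure**

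Inputs from Protocol 10.1: about 20 completers, and coefficients of variation for AUC(0-τ) and Cmax that "were 21.9% and 40.3%, respectively, after the initial dose, and 29.6% and 31.1%, respectively, at steady state". The stated result is an upper 95% limit within about 15% (AUC) and 20% (Cmax) above the estimate. SAP 7.1.4.1 reports a 95% CI for the geometric mean, so the log scale is used:

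upper limit = exp(t × σ / √n) − 1, with σ = √ln(1 + CV²) and t the 0.975 quantile on n − 1 degrees of freedom.

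Day 1 Cmax: σ = √ln(1 + 0.403²) = 0.388, and exp(2.093 × 0.388 / √20) − 1 = 19.9%. The other three at n=20 are 10.7% (Day 1 AUC), 14.5% (steady-state AUC) and 15.3% (steady-state Cmax). The stated 15% and 20% are reproduced.

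**Step 3. What the restriction costs in width**

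| n | Day 1 AUC | Day 1 Cmax |
|---|---|---|
| 19 | 11.0% | 20.6% |
| 20 | 10.7% | 19.9% |
| 23 | 9.8% | 18.3% |
| 25 | 9.3% | 17.4% |
| 30 | 8.4% | 15.6% |

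The rows for 25 and 30 assume that every enrolled participant has a valid Day 1 profile, so they show the largest possible gain over n=20: 1.3 to 2.2 points for AUC and 2.5 to 4.3 points for Cmax. If only 2 of 25 stop, the Cmax limit is 18.3% instead of 17.4%, under one point.

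The lack of slack for Day 1 Cmax depends on the scale. With t × CV / √n on the arithmetic scale, the limit is 18.9% at n=20 and 19.4% at n=19.

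**Step 4. Possible bias (illustration)**

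Protocol 5.2: "Approximately 25 to 30 participants will be enrolled to achieve approximately 20 participants who complete the study assessments through Day 5". The margin is (25 − 20)/25 = 20% to (30 − 20)/30 = 33%, used here as an upper bound on the excluded fraction f. Let g be the Day 1 geometric mean of excluded participants relative to completers. The documents give no value for g, so it is varied as an assumption. Completers-only over all-participant geometric mean = g^(−f):

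| g | f = 20% | f = 33% |
|---|---|---|
| 1.5 | 0.922 | 0.874 |
| 1.2 | 0.964 | 0.941 |
| 1.0 | 1.000 | 1.000 |
| 1/1.2 | 1.037 | 1.063 |
| 1/1.5 | 1.084 | 1.145 |

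With 2 of 22 excluded (f = 9.1%), g = 1.2 gives 0.984 and g = 1.5 gives 0.964.

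**The case against.** The best defence is that the rule is deliberate and harmless. It is prespecified identically in both documents, in a study that estimates and tests nothing. One cohort for Day 1, Day 4 and the within-participant ratio Ro makes the columns directly comparable. Precision was planned on about 20 completers, replacements are allowed (Protocol 5.2), and five days of supervised dosing in confinement may make stopping rare. Adverse events and QTc are analysed in the Safety Population, which keeps everyone who took a dose.

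Most of this stands and limits the size of the point. It does not supply a reason to omit a completed Day 1 profile. Comparability is served equally well by showing the common cohort as a second display.

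Two SAP passages could be read as already keeping these data. Section 7.1.3 names both populations, but section 4 reserves the PK Population for concentrations and the PK Parameter Population for parameters. Section 12.5.1 includes available non-efficacy data from withdrawn participants unless something else is specified. The population definition does specify something else, and under Protocol 8.1 and 8.1.3 those who stop treatment are not counted as withdrawn. Neither passage overrides the definition, though together they leave room for inconsistent programming.

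**Conclusion.** The point holds as a cheap improvement. By its wording, the definition omits valid Day 1 plasma and urine parameters of early stoppers from the summaries and listings, and omits both profiles of anyone who stops between Day 4 sampling and the Day 5 predose draw. The Day 1 intervals are wider than they need be, by at most 4.3 points for Cmax and 2.2 for AUC, and the estimates may be biased.

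A reader might infer more, but the documents do not support it:

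- *That Day 1 exposure will be understated.* Bias needs a link between stopping and exposure, which the documents do not establish. Its direction is open: adverse events or QTc stops could remove high exposures, and lack of efficacy could remove low ones.
- *That 20% to 33% will stop.* This is an enrolment margin. It also has to cover missed samples and profiles that cannot be evaluated, which a new definition need not recover.
- *That planned precision is lost.* It is met at n=20, although on the log scale Day 1 Cmax has almost no slack.
- *That the data are discarded.* The concentrations, and hence the observed peaks, remain displayed and listed.
- *That the PK/PD analysis is seriously affected.* SAP section 10 uses Day 4 parameters, so only those stopping between Day 4 sampling and the Day 5 predose draw are lost to it by this rule.

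**What to change.** In SAP section 4, with a note in SAP 2.1, define evaluability by day and parameter:

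- Day 1 plasma and urine parameters: all participants with a complete first dose and an evaluable Day 1 profile.
- Day 4 parameters and CLss/F: participants dosed as planned through the Day 4 time-matched dose, with an evaluable Day 4 profile.
- Ro: participants meeting the Day 4 condition who also have an evaluable Day 1 profile.

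Show the completers-only Day 1 summary as a sensitivity display. Reconcile SAP 7.1.3 and 12.5.1 with the new wording, so that each parameter is tied to one set.

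The cost is a few lines of SAP text and one extra display. No new data or change in sample size is needed. The downside is that n will differ between the Day 1 and Day 4 columns, which a table footnote can explain.

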4.1. Protocol Deviations

Significant protocol deviations (including deviations related to study inclusion/exclusion criteria, conduct of the trial, patient management or patient assessment) will be summarised and listed.

Protocol deviations will be tracked by the study team throughout the conduct of the study in accordance with the Protocol Deviation Management Plan.

- Data will be reviewed prior to freezing the database to ensure all significant deviations and deviations which may lead to exclusion from the analysis are captured and categorised on the protocol deviations dataset.

- This dataset will be the basis for the summaries and listings of protocol deviations.

A separate listing of all inclusion/exclusion criteria deviations will also be provided. This listing will be based on data as recorded on the inclusion/exclusion page of the electronic case report form (eCRF).

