12.4.2. Study Population

Age

 • GSK standard IDSL algorithms will be used for calculating age where birth date will be imputed as follows: 
 ○ Any subject with a missing day will have this imputed as day ‘15’. ○ Any subject with a missing day and month will have this imputed as ‘30th June’. • Birth date will be presented in listings as ‘YYYY’.
Body Mass Index (BMI)

 • Calculated as Weight (kg) / Height (m)²
Micro-ITT Population

 • Micro-ITT population include participants who receive at least 1 dose of gepotidacin and have a qualifying bacterial uropathogen at Baseline from a quantitative bacteriology culture of a pretreatment clean-catch midstream urine specimen. • The algorithm of the qualifying bacterial uropathogen is presented in Figure 2. If there're 2 uropathogens identified at baseline for a participant, the participant will be included in the micro-ITT population if at least 1 of the 2 uropathogens is ≥10⁵ CFU/mL.

Figure 2 Baseline Algorithm for the Microbiological intent-to-Treat Population

CFU=colony-forming units; micro-ITT=Microbiological Intent-to-Treat.

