12.9.12. ICH Listings

ICH: Listings					
No.	Population	IDSL / Example Shell	Title	Programming Notes	Deliverable
Subject Disposition					
1.	Intent-to-Treat	ES2	Listing of Reasons for Study Withdrawal		DS, SAC
2.	Intent-to-Treat	SD2	Listing of Reasons for Study Treatment Discontinuation		DS, SAC
3.	Intent-to-Treat	SP3	Listing of Subjects Excluded from Any Population		DS, SAC
Protocol Deviations					
4.	Intent-to-Treat	DV2	Listing of Significant Protocol Deviations		DS, SAC
5.	Intent-to-Treat	IE3	Listing of Subjects with Inclusion/Exclusion Criteria Deviations		DS, SAC
Demographic and Baseline Characteristics					
6.	Intent-to-Treat	DM2	Listing of Demographic Characteristics		DS, SAC
7.	Intent-to-Treat	DM9	Listing of Race		DS, SAC
8.	Intent-to-Treat	SAFE_L1	Listing of History of Uncomplicated Urinary Tract Infection		DS, SAC
9.	Intent-to-Treat	MH2	Listing of Medical Conditions		DS, SAC

ICH: Listings					
No.	Population	IDSL / Example Shell	Title	Programming Notes	Deliverable
Prior and Concomitant Medications					
10.	Intent-to-Treat	CM3	Listing of Prior and Concomitant Medications		DS, SAC
Exposure and Treatment Compliance					
11.	Intent-to-Treat	EX3	Listing of Exposure Data		DS, SAC
Efficacy					
12.	Intent-to-Treat	EFF_L1	Listing of Clinical Outcome and Response		DS, SAC
13.	ITT	EFF_L2	Listing of Urine Specimen Gram Stain Results		DS, SAC
14.	ITT	EFF_L2	Listing of Urine Quantitative Bacteriology Culture Results		DS, SAC
15.	ITT	EFF_L3	Listing of Susceptibility Results		DS, SAC
16.	Intent-to-treat	EFF_L4	Listing of Gepotidacin MIC Result, Sponsor-Determined Clinical Response, Microbiological Outcome and Response, and Therapeutic Response by Uropathogen Isolated at Baseline	Page by participants in micro-ITT population and participants not in micro-ITT population	DS, SAC
Adverse Events					
17.	Safety	AE2	Listing of Relationship Between System Organ Class and Verbatim Text		DS, SAC
18.	Safety	AE7	Listing of Subject Numbers for Individual Adverse Events		DS, SAC
19.	Safety	AE8CP	Listing of All Adverse events		DS, SAC
Serious and Other Significant Adverse Events					
20.	Safety	AE8CP	Listing of Study Drug Related Adverse Events		DS, SAC
21.	Safety	SAFE_L2	Listing of Serious Adverse Events (Fatal & Non-Fatal)		DS, SAC

ICH: Listings					
No.	Population	IDSL / Example Shell	Title	Programming Notes	Deliverable
22.	Safety	AE8CP	Listing of Adverse Events Leading to Discontinuation of Study Treatment or Withdrawal from Study		DS, SAC
All Laboratory					

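### SAP section 4 adds an undeclared eligibility condition to the protocol's ITT; read literally, it conflicts with the SAP's own micro-ITT definition and drops treated ineligible women from the displays meant to show them

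*SAP*

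**What the plan says.** **ITT.** Protocol section 10.2 has "All participants assigned to study treatment". SAP section 4 has "All participants that met all eligibilities and were assigned to study treatment". The table of changes in SAP section 2.1 has two entries, the sponsor-determined clinical outcome and clinical cure. ITT is not among them.

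**Micro-ITT.** Protocol section 10.2 has "All participants assigned to study treatment who receive at least 1 dose of gepotidacin have a qualifying baseline uropathogen", and protocol Appendix 9 likewise asks only for a dose and a qualifying uropathogen. SAP section 4 starts instead from ITT: "All participants in the ITT Population, receive at least 1 dose of gepotidacin", plus a qualifying uropathogen. SAP section 12.4.2 restates the set without ITT and without eligibility: "Micro-ITT population include participants who receive at least 1 dose of gepotidacin and have a qualifying bacterial uropathogen at Baseline". The SAP's PKPD population is the overlap of PK Parameter and micro-ITT.

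**Deviation reporting.** SAP section 4.1 promises "Significant protocol deviations (including deviations related to study inclusion/exclusion criteria, conduct of the trial, patient management or patient assessment) will be summarised and listed". It adds "A separate listing of all inclusion/exclusion criteria deviations will also be provided", taken from the inclusion/exclusion page of the eCRF. In SAP section 12.9, the summary of significant deviations (Table 1.3), the listing of participants excluded from any population (Listing 3), the listing of significant deviations (Listing 4) and the "Listing of Subjects with Inclusion/Exclusion Criteria Deviations" (Listing 5) are all assigned to ITT. So are the disposition, demographic and exposure displays.

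**The concern.** An ITT population for a single-arm study should be fixed by entry to treatment. Adding an eligibility condition allows a woman to be dosed, followed and then removed because of something discovered afterwards. Three things are at stake.

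- The two SAP definitions of micro-ITT can select different women, and a programmer cannot follow both.
- The displays meant to show eligibility deviations run on a set that, taken at its word, contains nobody with such a deviation.
- Safety may contain women who have adverse-event and laboratory displays but no place in the disposition, demographic or exposure displays. Removing women from the efficacy sets for eligibility findings could also move the response rates in either direction.

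**Working it through.** **1. One participant under each definition.** Take a woman who was assigned and dosed, had a qualifying baseline uropathogen, and was later found not to meet a criterion. Read 'met all eligibilities' literally, as actual eligibility or as recorded on the eCRF eligibility page.

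| Set | Source | Eligibility condition | She is |
|---|---|---|---|
| ITT | Protocol 10.2 | none | in |
| ITT | SAP 4 | yes | out |
| Micro-ITT | Protocol 10.2, Appendix 9 | none | in |
| Micro-ITT | SAP 4 | inherited from ITT | out |
| Micro-ITT | SAP 12.4.2 | none | in |
| PKPD | SAP 4 | inherited from micro-ITT | out |
| Safety | Protocol 10.2, SAP 4 | none | in |
| PK, PK Parameter | SAP 4, built on Safety | none | in, if her data are evaluable |

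The two SAP rows for micro-ITT disagree.

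**2. Displays on the literal reading.**
- Listing 5 = (assigned and met all criteria) ∩ (failed at least one criterion), which is the empty set. Of the 16 combinations of eligible, assigned, dosed and culture-positive, none gives an entry. Under the protocol's ITT, every assigned and ineligible combination does.
- Listing 3 runs on ITT, so it cannot name a woman excluded from ITT itself.
- Table 1.3 and Listing 4 lose all deviations of the excluded women. They need not be empty, because other women can have other kinds of deviation.
- Tables 1.1 to 1.9 omit her. SAP section 4 names study-population analyses against Safety as well as ITT, but every study-population table in section 12.9.4 is labelled ITT.
- All nine efficacy tables in section 12.9.5 run on ITT or micro-ITT.

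**3. Size of the gap between Safety and ITT.** The documents do not say how many treated women might prove ineligible. Assume 1 to 3 among the planned 25 to 30, all dosed. The gap is k/N, from 1/30 = 3.3% to 3/25 = 12.0%.

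**4. Effect on a response rate.** The documents give no micro-ITT size. Assume 10 or 20 participants and 80% success, with one woman removed. Intervals are 95% Clopper-Pearson, the SAP's method.

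| Assumed micro-ITT | All | One failure removed | One success removed |
|---|---|---|---|
| 10 | 8/10 = 80.0% (44.4 to 97.5) | 8/9 = 88.9% (51.8 to 99.7) | 7/9 = 77.8% (40.0 to 97.2) |
| 20 | 16/20 = 80.0% (56.3 to 94.3) | 16/19 = 84.2% (60.4 to 96.6) | 15/19 = 78.9% (54.4 to 93.9) |

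**5. What is untouched.** The plan's only sample-size figure is the PK precision in protocol section 10.1: upper 95% limits within about 15% (AUC) and 20% (Cmax) above the estimate, with 20 completers. It reproduces as t(0.975, 19) × CV / √20. For AUC at steady state, 2.093 × 29.6% / 4.472 = 13.9%. For Cmax on Day 1, 2.093 × 40.3% / 4.472 = 18.9%. It does not depend on ITT, since PK and PK Parameter are built on Safety.

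**The case against.** The strongest reply is that the phrase only describes the enrolment step. Protocol section 7.3 has clinic staff enrol a participant after she has met the eligibility requirements, and protocol section 6 forbids waivers. On that reading SAP and protocol ITT contain the same women, the two micro-ITT definitions agree, and a violation found after dosing stays in ITT and appears in Listing 5. Putting eligibility-deviation displays on ITT makes better sense this way.

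This stands as a possible reading, so the inference that Listing 5 will be empty whatever happens goes too far. It does not rescue the wording. The SAP never says that site judgement is meant, section 4.1 itself expects eligibility deviations, and a ban on waivers cannot prevent a later discovery. If site judgement is meant, the words add nothing to being assigned.

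Three other stronger inferences also fail.
- **That excluded women would be invisible in the report.** SAP section 12.5.2 requires anyone excluded from summaries or analyses to be documented with the reason in the study report, and section 4.1 has deviations that may lead to exclusion captured before database freeze. The women also remain in all Safety displays.
- **That ITT has become a post-hoc per-protocol set.** The condition is written into the SAP and concerns entry criteria only, not compliance, visits or outcome. There is no randomised comparison to break.
- **That micro-ITT will hold about 20 women.** Twenty is the target for PK-evaluable completers. Micro-ITT also depends on baseline culture, for which no positivity rate is given.

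**Conclusion.** The ITT definition in SAP section 4 is wrong as written. It departs from the protocol without being declared. Taken literally, it contradicts SAP section 12.4.2 on micro-ITT, carries the exclusion into PKPD, and defeats Listings 3 and 5 while leaving Table 1.3, Listing 4 and the study-population displays incomplete. Taken as the site's enrolment decision, it is redundant. Both readings call for the same edit.

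The consequence is limited. The primary plasma PK, secondary urine PK and safety analyses do not use ITT. Efficacy is exploratory, with no hypothesis test and no comparator. The numerical effect on response rates cannot be established from the documents: the figures above assume the number of ineligible women, the micro-ITT size and the success rate, and the direction depends on who is removed. The definitional and reporting defect does not depend on those assumptions.

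**What to change.** In SAP section 4, restore the protocol's ITT, "All participants assigned to study treatment", by deleting the eligibility condition. Align micro-ITT in section 4 with SAP section 12.4.2 and protocol Appendix 9, so that one definition governs the efficacy and PKPD displays. Table 1.3 and Listings 3 to 5 then work as labelled.

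If an eligible-only set is wanted, declare it in SAP section 2.1 with a rationale, use it as a sensitivity analysis, and run Table 1.3 and Listings 3 to 5 on all assigned participants.

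The basic correction is a text edit that needs no new data. The optional sensitivity analysis would add a repeat of the relevant efficacy summaries.
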